11.0 Pharmacokinetic Analyses

11.1 Tabulations and Summary Statistics

Summary statistics of plasma concentrations of venetoclax and ibrutinib will be computed for each sampling time. Pharmacokinetic parameter values of venetoclax and ibrutinib will be summarized as applicable. Additional analyses will be performed if useful and appropriate.

12.0 Interim Analyses

There is no planned interim efficacy analysis for this study. However, a safety analysis of tolerability of the venetoclax and ibrutinib combination will be performed after the first 6 evaluable subjects have been on the combination for a minimum of 5 weeks and at least 1 week of venetoclax dosed at 400 mg.

12.1 Independent Safety Monitor

For DLT assessments of the first 6 evaluable subjects enrolled, sponsor will appoint an Independent Safety Monitor (ISM), who will be a Japan medical oncologist with experience in clinical studies and who is familiar with the safety assessment of antitumor agents. The Sponsor will consult the Independent Safety Monitor (ISM) with results of the safety evaluation and Sponsor's conclusion on tolerability, then receive the answer from ISM. The Sponsor will recommence subject enrolment based on the safety review and only if agreed by the ISM. Depending on the results of the safety review by ISM, revising the protocol will be considered where necessary. Detailed procedures for safety assessments will be described in a separately prepared document for operational purposes.

Since only safety and PK data (if available at the time of tolerability assessment meeting) are to be assessed for DLT, so no alpha adjustment is needed.

13.0 Overall Type-I Error Control

The overall type I error rate of 1-sided 0.025 will be used to determine the statistical significance of the primary endpoint at the time of primary analysis. All other analyses will be done for descriptive purpose. Hence, no multiplicity adjustment of type I error is needed.

14.0 Version History

Table 3. SAP Version History Summary

Version	Date	Summary
1.0	12 Nov 2020	Original version
2.0	16 Apr 2022	Amendment 1

Appendix A. Protocol Deviations

A listing of subjects who reported at least one (but not limited to) of the following protocol deviation categories will be provided.

- Subject entered into the study even though s/he did not satisfy entry criteria.
- Subject developed withdrawal criteria during the study and was not withdrawn.
- Subject received wrong treatment or incorrect dose of study.
- Subject took prohibited concomitant medication.

Appendix B. Definition of Adverse Events of Special Interest

Adverse Events of Special Interest (AESI) and Selected AEs will be identified using the following search criteria:

Risk	Search Criteria
Tumor Lysis Syndrome	SMQ 20000219 – "Tumour lysis syndrome" (Narrow-scope)
Neutropenia – expanded search	Neutropenia CMQ 80000171
Neutropenia	PT terms – "Neutropenia" and "Neutrophil count decreased"
Serious Infection	SAEs in the SOC of "Infections and Infestations"
Second Primary Malignancy	SMQ 20000194 – "Malignant tumours" (Narrow) and SMQ 20000217 - "Myelodysplastic syndromes" (Narrow)
Lymphopenia	PT terms – "Lymphopenia" and "Lymphocyte count decreased"
Anemia	PT terms – "Anaemia" and "Haemoglobin decreased"
Thrombocytopenia	PT terms – "Thrombocytopenia" and "Platelet count decreased"
Major Hemorrhage	SMQ – "Haemorrhagic disorders" (narrow)
Cardiac arrhythmia	
1. Atrial fibrillation: PT= Atrial fibrillation2. Cardiac arrhythmias: Cardiac arrhythmias SMQ broad (excluding PT of Atrial fibrillation)3. Ventricular tachyarrhythmias (as a sub-analysis under Cardiac arrhythmias recognizing there is overlap): Ventricular tachyarrhythmias SMQ narrow

Appendix C. Potentially Clinically Important Criteria for Safety**Table C-1. Criteria for Potentially Clinically Important Vital Sign Values**

Vital Signs Variables	Criterion	Definition of Potentially Clinically Significant
Systolic blood pressure	High	Value \geq 160 mmHg
Diastolic blood pressure	High	Value \geq 100 mmHg
Heart rate (bpm)	Low	Value < 50 bpm
	High	Value \geq 120 bpm
Temperature	Low	Value < 36°C
	High	Value \geq 38.0°C

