 - For the purpose of TLS assessment during the DLT evaluation period, only those increases in serum creatinine > 1.0 mg/dL from pre-treatment baseline will be considered clinical TLS.
 - In subjects with renal dysfunction at baseline (CrCl < 60 mL/min), clinical TLS is defined as the presence of laboratory TLS plus either seizures, cardiac dysrhythmia, or death.
- Laboratory TLS: any event that meets Howard criteria ([Appendix G](#)) for laboratory TLS, that does not resolve within 72 hours despite protocol required management.

Major hemorrhage events are defined as:

- Any treatment-emergent Grade \geq 3 hemorrhage AEs (all hemorrhagic events requiring transfusion of red blood cells should be reported as Grade 3 or higher AE per National Cancer Institute (NCI) CTCAE v5.0).
- Any treatment-emergent SAEs of bleeding of any grade
- Any treatment-emergent CNS hemorrhage/hematoma of any grade.

Adverse Event Severity and Relationship to Study Drug

The investigator will rate the severity of each AE according to the NCI CTCAE Version 5.0. If a reported AE increases in severity, the initial event should be given an outcome date and a new AE must be reported to reflect the change in severity. For all reported SAEs that increase in severity, the supplemental eCRFs also need to be updated to reflect any changes due to the increase in severity.

For AEs not captured by the NCI CTCAE, the following criteria should be used:

Grade 1	Mild; asymptomatic or mild symptoms; clinical diagnostic observations only; intervention not indicated.
Grade 2	Moderate; minimal, local or noninvasive intervention indicated; limiting age-appropriate instrumental activities of daily living.
Grade 3	Severe or medically significant but not immediately life-threatening; hospitalization or prolongation of hospitalization indicated; disabling; limiting self-care activities of daily living.
Grade 4	Life-threatening consequences; urgent intervention indicated.
Grade 5	Death related to adverse event.

The investigator will use the following definitions to assess the relationship of the AE to the use of study drug (venetoclax and ibrutinib):

Reasonable Possibility	After consideration of factors including timing of the event, biologic plausibility, clinical judgment, and potential alternative causes, there is sufficient evidence (information) to suggest a causal relationship.

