10.2.5 Adverse Events of Special Interest

Adverse events of special interest will be summarized by SOC and PT and will be based on standardized or company MedDRA queries (SMQs or CMQs). Adverse events of special interest along with the detailed information about the search criteria are provided in [Appendix B](#). Tabular listings of selected adverse events of special interest will be provided.

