2. Shifts from grade 0 – 2 at baseline to grade 3 or 4 post-baseline (maximum) and from grade 3 at baseline value to grade 4 post-baseline (maximum).

For above shift tables, baseline grade of 0 (normal) will be imputed for all subjects with at least one post-baseline but missing a baseline value for each lab test.

Detailed listings of data for subjects experiencing NCI CTCAE Grade 3 to 4 blood chemistry and hematology values will be provided. All measurements collected, regardless of the number of days after the last dose of study drug, will be included in these listings.

Number and percentage of subjects meeting the Howard criteria for tumor lysis syndrome (TLS) will be presented.

The Howard Criteria for TLS is defined as two or more of the following treatment-emergent lab changes within a 24-hour period. The evaluation period for TLS is the first 7 days from the date of the first dose:

- Uric Acid > 475.8 mcmol/L,
- Potassium > 6 mmol/L,
- Inorganic Phosphorus > 1.5 mmol/L
- Calcium < 1.75 mmol/L.

TLS events are defined as:

- Clinical TLS: any event that meets Howard criteria with the following exceptions:
 - For the purpose of TLS assessment during the DLT evaluation period, only those increases in serum creatinine > 1.0 mg/dL from pre-treatment baseline will be considered clinical TLS.
 - In subjects with renal dysfunction at baseline ($\text{CrCl} < 60$ mL/min), clinical TLS is defined as the presence of laboratory TLS plus either seizures, cardiac dysrhythmia, or death.
- Laboratory TLS: any event that meets Howard criteria for laboratory TLS, that does not resolve within 72 hours despite protocol required management.

A listing of possible Hy's Law cases, defined as those who meet all of the following conditions simultaneously, will be provided: $\text{ALT} > 3 \times \text{ULN}$ or $\text{AST} > 3 \times \text{ULN}$ that is associated with an increase in bilirubin $> 2 \times \text{ULN}$ within 72 hours of each other.

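### SAP Appendix B labels every bleed found by the narrow SMQ as major hemorrhage, without the Grade 3 or higher, serious or CNS conditions of protocol 6.1

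*SAP*

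**What the plan says.** Protocol 6.1 lists tumor lysis syndrome (TLS) and major hemorrhage as the adverse events of special interest. A treatment-emergent bleeding event is major if it meets any one of three conditions:

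- It is Grade 3 or higher. To support this, "all hemorrhagic events requiring transfusion of red blood cells should be reported as Grade 3 or higher AE".
- It is serious: "Any treatment-emergent SAEs of bleeding of any grade".
- It is in the CNS: "Any treatment-emergent CNS hemorrhage/hematoma of any grade".

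SAP 10.2.5 says that AESIs "will be summarized by SOC and PT and will be based on standardized or company MedDRA queries (SMQs or CMQs"), and refers to SAP Appendix B for the search criteria. The whole criterion in the Major Hemorrhage row there is "SMQ – 'Haemorrhagic disorders' (narrow" scope. The row does not refer back to protocol 6.1, and hemorrhage appears nowhere else in the SAP.

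**The concern.** The SAP table uses the protocol's name for the event but selects events by a different rule. Narrow scope limits which MedDRA terms are searched. It does not limit grade or seriousness, and it does not single out CNS bleeding. A programmer following Appendix B would therefore place minor bleeds under a heading that the protocol reserves for a more severe category.

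At stake is the accuracy of one of the two AESI results that the protocol asks for. Bleeding is a known issue in this trial: protocol 5.3 urges caution with anticoagulants and antiplatelet agents, and protocol 5.5 warns of bleeding risk with procedures on ibrutinib. A reader of the study report would naturally take a figure labelled major hemorrhage to be the protocol-defined event. The primary endpoint and its test are not affected.

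**Working it through.** The SAP gives no figure to reproduce here. The check compares the texts, then works out the weight of one subject.

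**1. Condition by condition**

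| Protocol 6.1 condition (any one suffices) | In the Appendix B Major Hemorrhage row? |
|---|---|
| Grade 3 or higher | No |
| Serious, any grade | No |
| CNS hemorrhage or hematoma, any grade | No |

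The row carries 0 of the 3 conditions.

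**2. Could the table have held a filter?** Appendix B has 10 rows: TLS, neutropenia (expanded search), neutropenia, serious infection, second primary malignancy, lymphopenia, anemia, thrombocytopenia, major hemorrhage and cardiac arrhythmia. One row has a seriousness condition, the Serious Infection row: "SAEs in the SOC of 'Infections and Infestations". None has a grade condition. The table format therefore allows a restriction, and one is written out for serious infection.

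**3. Is the definition supplied elsewhere in the SAP?** For TLS, yes. Its Appendix B row is also a bare query, "SMQ 20000219 – 'Tumour lysis syndrome' (Narrow-scope"), but SAP 10.3 restates the protocol's definitions, for example "Laboratory TLS: any event that meets Howard criteria for laboratory TLS, that does not resolve within 72 hours despite protocol required management". Hemorrhage has no such restatement.

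**4. Which events are misplaced?** An event is misplaced if it is coded to the query, non-serious, Grade 1 or 2, and outside the CNS. It meets no protocol condition but meets the Appendix B criterion. In the other direction, a Grade 3 or higher or serious bleed coded to the query is still captured. Whether the query returns every CNS hemorrhage or hematoma term cannot be checked, because the documents do not list its terms.

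**5. Weight of one subject.** SAP 10.1 summarizes safety on the full analysis set. For k subjects whose only bleeds are misplaced ones, the overstatement in the proportion with major hemorrhage is k/N.

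- N = 12, the planned number (protocol 7.7): 1/12 = 8.3 points per subject.
- N = 13, assuming one subject is added under the provision in protocol 7.7 for disease that the IRC finds non-evaluable at baseline: 1/13 = 7.7 points per subject.

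The documents do not give k. If k is assumed, purely for illustration, to lie between 0 and 4, the overstatement with N = 12 runs from 0 to 4/12 = 33.3 points.

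A subject who also has a qualifying bleed does not change the subject-level proportion. That subject's minor bleeds would still appear as preferred terms under the major hemorrhage heading.

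**The case against.** The case for leaving this alone is that little depends on it. SAP 13.0 makes every analysis other than the primary one descriptive. The overview in SAP 10.2.2 has no hemorrhage row, and no confidence interval is planned for this AESI. The decision to continue enrollment used the DLT criteria in protocol 6.3, not Appendix B. The AESI summary is by SOC and preferred term, so each bleed stays visible. SAP 10.2.3 and 10.2.4 add tables by maximum grade and by subject number, and SAE summaries and listings. Appendix B also covers selected AEs beyond the protocol's two AESIs, and most of its rows are plain term searches.

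Most of this stands, and it limits the consequence. It does not make the labelled figure right. To rebuild the protocol's count, a reader would have to combine grade, seriousness and CNS site subject by subject without a CNS term list. SAP 10.2.5 promises listings only for selected AESIs, so a hemorrhage listing is not assured. The appendix is also headed as the definition of these events, which makes it hard to read as a mere search list.

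A second objection concerns versions. SAP 1.0 says that it was written for protocol version 3.0, which is not supplied. The change summary in protocol Appendix J lists no change to the hemorrhage definition, but it covers only the step from version 4.0 to the current version. The mismatch is therefore shown against the current protocol only. Whether the SAP also departed from version 3.0 cannot be settled.

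**Conclusion.** The mismatch is real. Following the SAP as written yields a result labelled major hemorrhage that can include bleeds the current protocol does not count as major. Each subject whose only bleeds are non-qualifying adds 8.3 points with 12 subjects, or 7.7 with 13. The total is unknown because the documents give no bleeding rate.

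This should be corrected, but it is not critical: it affects one descriptive safety summary, and the data to repair it are already collected. The conclusion rests on the current protocol's definition and on reading Appendix B literally. It does not depend on which terms the query contains, beyond its being a bleeding query that returns some events of low grade.

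**What to change.** In SAP Appendix B, define Major Hemorrhage as treatment-emergent hemorrhage events that are Grade 3 or higher, or serious, or CNS hemorrhage or hematoma of any grade.

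- **CNS condition.** Specify a list of CNS preferred terms that is not limited to what the SMQ returns, because the protocol counts any CNS bleed.
- **Unfiltered query.** Keep it if wanted, as a separate row named any hemorrhage.
- **Grade.** State that the filter uses the grade recorded by the investigator. Protocol 6.1 grades by CTCAE 5.0, while SAP 10.2.2 and 10.3 cite 4.03, so the two should be reconciled at the same time.
- **Existing output.** Protocol Appendix J reports that the primary analysis is complete. Rerun any AESI tables already produced, or footnote them to say that the row shows all bleeds in the narrow SMQ.

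The cost is one row of SAP wording, a short term list and a programming filter on grade and seriousness. No new data are needed, since bleeds that require red-cell transfusion are already to be reported as Grade 3 or higher.
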